7.2.3 Number of Subjects Required

A total of up to 20 newly implanted subjects is planned. This sample size should provide adequate power for statistical tests of the primary endpoint under conservative assumptions.

7.2.4 Vulnerable Populations

Not applicable.

7.2.5 Enrollment & Study Duration

The following subject status definitions apply:

Consented: A subject who has provided informed consent and is being assessed for eligibility according to the Screening requirements.

Screen Fail: A consented subject that has been determined to not meet all eligibility criteria for enrolment.

Enrolled/Treated: Subjects who have met all eligibility criteria, have qualified for surgery and have received the Osia 2 implant.

Withdrawn: Enrolled subjects who withdraw or are withdrawn by the Investigator or Sponsor before their expected end of study visits. Withdrawn subjects may still continue in safety follow-up until their scheduled end of study visit for reasons described in section 7.2.6.

The enrollment period for the clinical investigation is anticipated to be 6 - 8 months from the time of first subject consent to enrollment of the last subject.

The expected duration of each subject's participation is 7-8 months.

During this time there will be required research related visits.

- Screening
- Visit 1
- Visit 2: Surgery - Treatment
- Visit 3: 2-week check post-surgery
- Visit 4: 4-week post-surgery fitting
- Visit 5: 3 Months post-surgery
- Visit 6: 6 Months post-surgery (End of Study)

The anticipated total duration of the clinical investigation is therefore 12 - 18 months including set up, execution and closure. The execution phase of the Clinical Investigation is considered complete after the last subject, last visit. IRBs should remain open through closeout monitoring activities, until Sponsor notifies site of database lock.

7.2.6 Criteria for Subject Withdrawal

Subjects can decide to withdraw from the investigation at any time. The Investigator shall ask the reason(s). The reason for withdrawal should be documented in the subject's source files and the case report form (CRF).

The Investigator or Sponsor may also decide to withdraw a subject from the clinical investigation if it is considered to be in their best interests.

Subject withdrawal may be for any of the following reasons:

- Adverse Event (AE)

- Device Deficiency (DD)
- CIP or GCP deviation
- Subject lost to follow-up
- Subject withdrew consent
- Subject death
- Sponsor decision
- Investigator decision
- Other (specify)

If subject withdrawal is due to problems related to the AMDT or comparator safety or performance, the Investigator shall ask for the subject's permission to continue in safety follow up (i.e., adverse events) until their scheduled End-of-Study visit.

If a subject is lost to follow-up, every possible effort must be made by the study site personnel to contact the subject and determine the reason for discontinuation. At least 3 separate attempts taken to contact the subject may be documented in the medical chart.

Treated subjects who are withdrawn/discontinued will not be replaced.

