3 SCHEDULE OF EVENTS

	Screening	Visit 1	Visit 2	Visit 3	Visit 4	Visit 5	Visit 6 EOS
Timing of Investigation	Day -1	Day -1	Day 0	Week 2	Week 4	Month 3	Month 6
Visit window (±)	NA	± 0 days	± 0 days	± 5 days	± 7 days	± 7 days	± 7 days
Time Estimation	2 hrs. 15 mins.	3 hrs. 15 mins	1 hr.	1 hr.	3 hrs.	4 hrs.	3 hrs.
Written informed consent	X						
Demographics	X						
Inclusion/Exclusion	X						
Hearing history	X						
Medical history	X						
Audiogram	X						
Concomitant Medications ¹		X	X	X	X	X	X
Sound field thresholds		X ²			X ³	X ⁴	X
Speech perception testing in quiet		X ⁵			X ⁶	X ⁷	X

¹ Collected post-Visit 1 only if changes to prescription concomitant medications associated with device or procedure-related adverse event.

² Includes sound field thresholds, unaided and aided, with Baha 5 Power on Sound Arc.

³ Visits 4 & 6 include sound field thresholds, aided, with Osia Sound Processor.

⁴ Visit 5 includes sound field thresholds, unaided and aided, with Osia Sound Processor.

⁵ Includes speech in quiet testing, unaided and aided, with Baha 5 Power on Sound Arc.

⁶ Visits 4 & 6 include speech perception in quiet, aided, with Osia Sound Processor.

⁷ Visit 5 includes speech perception in quiet, unaided and aided, with Osia Sound Processor.

	Screening	Visit 1	Visit 2	Visit 3	Visit 4	Visit 5	Visit 6 EOS
Timing of Investigation	Day -1	Day -1	Day 0	Week 2	Week 4	Month 3	Month 6
Visit window (±)	NA	± 0 days	± 0 days	± 5 days	± 7 days	± 7 days	± 7 days
Time Estimation	2 hrs. 15 mins.	3 hrs. 15 mins	1 hr.	1 hr.	3 hrs.	4 hrs.	3 hrs.
Speech perception testing in noise +5 dB SNR		X ⁸				X ⁹	
Adaptive speech in noise testing		X ¹⁰			X ¹¹	X ¹²	X
SSQ 12		X				X	
Patient Reported Questionnaire		X				X	
Device Counseling		X			X		
Surgical Follow up				X			
Fitting and Optimization of Sound Processor		X ¹³			X ¹⁴	X	X
Device Deficiencies			X	X	X	X	X
Adverse Events			X	X	X	X	X
Data Entry	X	X	X	X	X	X	X

⁸ Includes speech perception in noise, unaided and aided, with Baha 5 Power on Sound Arc.

⁹ Visit 5 includes speech perception in noise, unaided and aided, with Osia Sound Processor.

¹⁰ Includes adaptive speech in noise testing, unaided and aided, with Baha 5 Power on Sound Arc.

¹¹ Visit 4 & 6 include adaptive speech in noise testing, aided, with Osia Sound Processor.

¹² Visit 5 includes adaptive speech in noise testing, unaided and aided, with Osia Sound Processor.

¹³ Fitting with Baha 5 Power on Sound Arc.

¹⁴ Fitting with Osia Sound Processor.

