7.5 Sponsor Role in Conduct of the Clinical Investigation

Sponsor representatives may be present for intraoperative surgical support and clinical support of programming visits.

Sponsor representatives will be actively engaged in monitoring and operational communications with clinical sites for appropriate oversight and to ensure compliance. Further details regarding site communications and roles/responsibilities are documented in the Safety Data Handling Plan and Communications Plan.

To mitigate any potential bias, if it is requested that the Sponsor enter data into the electronic data capture system, the assigned individuals will not be involved in analysis of data. The Clinical Project Manager as well as the Clinical Review Board will be tasked with reviewing data listings for any abnormal trends associated with protocol compliance and/or safety issues. Formal analyses will be performed according to the Statistical Analysis Plan.

8 RISKS AND BENEFITS OF THE CLINICAL INVESTIGATION AND APPROVED MEDICAL DEVICE ON TEST

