9.4 Sample Size Determination

The planned sample size of 20 will provide greater than 95% power under a conservatively assumed mean of 12 and standard deviation of 15. Calculations are based on a one-sided 0.025 alpha and include allowance for attrition of up to 20%.

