4.3 Study Assessments

The statistical analyses for the primary objective will be based on the 3-month assessment compared to the pre-operative baseline assessment. Analyses for the secondary objective will be based on safety data collected at the time of treatment and for the duration of the study up to and including 6 months.

Statistical Analysis Plan		Page 8 of 13
Sponsor Cochlear Americas	Study A post-market interventional cohort study evaluating the clinical efficacy of the Osia 2 system in the US Market	Version 3.0

5 Sample Size Determination

The planned sample size of 20 will provide greater than 80% power under a conservatively assumed mean of 12 and standard deviation of 15. Calculations are based on a one-sided 0.025 alpha and include allowance for attrition of up to 20%.

The primary objective is to evaluate the performance of the Osia 2 system on an adaptive speech in noise test. A paired t-test of superiority for the adaptive speech in noise test, comparing the aided and unaided conditions at 3-months relative to the preoperative (Visit 1) unaided condition. The mathematical statement of this hypothesis test is written as:

$$H_0: \Delta On \geq \Delta Off$$

$$H_1: \Delta On < \Delta Off$$

where ΔOn is the mean change in the adaptive speech in noise test between the 3-month aided (On) condition and the preoperative (Visit 1) unaided condition, and ΔOff is the mean change in the adaptive speech in noise test between the 3-month unaided condition (Off) and the preoperative (Visit 1) unaided condition. Successful rejection of the null hypothesis indicates the aided performance of the Osia 2 system is superior to the unaided performance based on the adaptive speech in noise test.

The secondary objective is to evaluate the safety of the Osia 2 system in a group of adult newly implanted recipients. Descriptive statistics specifically counts and percentages of device or procedure related adverse events captured through 6 months post-surgery will be summarized.

6 Statistical Analyses

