6.6.1.2 Handling of Missing Data

In the event there are missing primary endpoint data the primary endpoint will be analyzed using a multiple imputation analysis. SAS PROC MI will be used to produce 100 imputed datasets. The imputed variable will be the difference between aided and unaided conditions at 3 months in the change in adaptive speech in noise test from preoperative. The following variables will be used as predictors in the model:

- Age
- Sex
- Pre-operative unaided adaptive speech in noise test

The estimates for the mean difference between aided and unaided change from pre-implant will be combined using PROC MIANALYZE providing an overall estimate for the primary endpoint, 95% confidence interval and one-sided p-value.

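### The plan collects no later speech-in-noise data from withdrawn implanted subjects and imputes Month 3 without the Visit 4 score, so withdrawal related to early device performance can bias the primary estimate toward the device

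*Protocol*

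**What the plan says.** **Withdrawal.** Protocol 7.2.6 lets the Investigator or Sponsor withdraw a subject when that is judged to be in the subject's best interests. It then lists reasons for withdrawal, among them "CIP or GCP deviation", Sponsor decision, Investigator decision and an open category. Treated subjects are not replaced. When the cause is a problem with the safety or performance of the test or comparator device, the Investigator asks the subject's permission to "continue in safety follow up (i.e., adverse events) until their scheduled End-of-Study visit". For every other reason the section is silent on later data.

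**What is known by then.** The study is unblinded (Protocol 7.2.8, SAP 4.2). On the primary test, the Schedule of Events states: "Visit 4 & 6 include adaptive speech in noise testing, aided, with Osia Sound Processor". Visit 4 is at Week 4; the primary endpoint is at Visit 5, Month 3. Protocol 7.5 adds: "Sponsor representatives may be present for intraoperative surgical support and clinical support of programming visits". It also gives the Sponsor's project manager and review board the task of reviewing data listings for compliance and safety trends.

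**Analysis.** The ITT set is everyone implanted, with multiple imputation of missing outcomes (Protocol 9.5, SAP 6.2). In SAP 6.6.1.2, "The following variables will be used as predictors in the model" introduces three items: age, sex and the preoperative unaided score. SAP 6.6.1.1, however, assesses the endpoint in ITT subjects whose preoperative and 3-month data are complete. Protocol 9.6 names sensitivity analyses for period and crossover effects only.

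**The concern.** A subject who leaves between Visit 4 and Visit 5 has one on-device measurement of the primary test, and the imputation model does not use it. If leaving is related to how the device performed at Visit 4, the outcome is missing at random only when the Visit 4 score is conditioned on. Without it, the imputed values resemble those of the subjects who stayed, who are then the better performers, and the estimate moves in the device's favour. This needs no bad faith: subjects who do poorly early may also miss procedures, disengage or ask to stop. With 20 subjects and no replacement, a few such losses matter. The study exists to support reimbursement (Protocol 4.2), so the size of the estimate matters as well as its significance.

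**Working it through.** **1. Scale.** Write the preoperative unaided score as U0 and the 3-month aided and unaided scores as A3 and U3. Then ΔOn − ΔOff = (A3 − U0) − (U3 − U0) = A3 − U3. The alternative is ΔOn < ΔOff, so lower scores are better. Below, benefit means U3 − A3, and positive bias favours the device.

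**2. The plan's own figures.** Protocol 9.4: "The planned sample size of 20 will provide greater than 95% power under a conservatively assumed mean of 12 and standard deviation of 15". Also: "Calculations are based on a one-sided 0.025 alpha and include allowance for attrition of up to 20" per cent. Attrition of 20% × 20 gives 4 lost and 16 evaluable. Exact paired-t power (noncentral t, n − 1 df, noncentrality (12/15)√n, one-sided 0.025) is 92.4% at n = 20 and 84.8% at n = 16. The Protocol's figure is not reproduced; it would need 23 evaluable subjects. SAP Section 5, on the same inputs, says "The planned sample size of 20 will provide greater than 80% power", which holds. That disagreement is a separate matter. Used here are N = 20, SD 15, mean 12, α = 0.025 and a planned ceiling of 4 missing.

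**3. Assumptions not in the documents.** The k poorest Visit 4 performers have no Month 3 value (k = 1, 2, 4). The correlation ρ between Visit 4 performance and Month 3 benefit is 0.3 to 0.7.

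**4. Complete-case bias.** With S_k the sum of the k largest expected normal order statistics in a sample of 20,

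bias = SD × ρ × S_k / (20 − k).

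- k = 1, S = 1.867: 15 × 1.867/19 = 1.474. Times ρ = 0.3, 0.5, 0.7: 0.44, 0.74, 1.03.
- k = 2, S = 3.275: 15 × 3.275/18 = 2.729. Times ρ: 0.82, 1.36, 1.91.
- k = 4, S = 5.327: 15 × 5.327/16 = 4.994. Times ρ: 1.50, 2.50, 3.50.

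Simulation agrees with these biases to within 0.02. The simulated rejection rates at a true benefit of 0 (nominal 2.5%) are:

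| Missing | ρ = 0 | ρ = 0.3 | ρ = 0.5 | ρ = 0.7 |
|---|---|---|---|---|
| 1 of 20 | 2.5% | 3.4% | 4.2% | 5.2% |
| 2 of 20 | 2.5% | 4.3% | 6.0% | 8.8% |
| 4 of 20 | 2.4% | 5.8% | 10.2% | 17.5% |

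**5. Multiple imputation.** Settings: 100 imputations, normal regression, Rubin's rules, baseline correlated 0.3 with benefit, 6,000 simulated trials per row. The SAP does not say which degrees of freedom apply, so error is shown as small-sample / large-sample.

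| Missing, ρ | Bias, SAP predictors | Error | Bias, Visit 4 added | Error |
|---|---|---|---|---|
| 1, 0.5 | +0.65 | 3.6% / 4.6% | −0.02 | 2.2% / 2.9% |
| 2, 0.5 | +1.27 | 5.1% / 6.9% | +0.05 | 2.4% / 3.5% |
| 4, 0.5 | +2.25 | 6.6% / 9.4% | −0.04 | 1.6% / 2.6% |
| 4, 0.7 | +3.21 | 12.3% / 15.8% | −0.04 | 2.2% / 3.1% |

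The SAP model removes little of the bias. Its error rates are below the complete-case ones with 4 missing. With 1 or 2 missing they fall slightly below or slightly above, depending on the degrees of freedom. Adding Visit 4 removes the bias.

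**6. At the planned effect.** With a true mean of 12 and 4 missing at ρ = 0.7, the complete-case estimate is 12 + 3.5 = 15.5, an overstatement of 3.5/12 = 29%. Power under selective loss is at least 92.5%, against 92.4% with no loss.

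**The case against.** **The withdrawal list is not a licence to remove poor performers.** It follows a best-interests condition and includes death and loss to follow-up, so it reads naturally as categories for recording why someone left. Sponsor-driven exits have non-selective uses: Protocol 17 closes sites for non-adherence or poor recruitment. Protocol 13 and SAP 6.11 document and summarise deviations, and SAP 6.1.2 keeps out-of-window visits. Withdrawal reasons are tabulated, so a pattern among 20 subjects would show. This stands. A reader might infer that the Sponsor will drop subjects because of their Visit 4 results; no section links withdrawal to those scores.

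**There is no conflict with ITT.** A reader might infer that withdrawing implanted subjects contradicts an all-implanted population. It does not: they stay in the set and their outcomes are imputed. The real inconsistency is the complete-data wording in SAP 6.6.1.1.

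**Adverse-event follow-up is not the general rule.** A reader might infer that a subject withdrawn for a deviation is followed for adverse events only. That clause covers device or comparator problems; for a deviation, 7.2.6 specifies nothing.

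**The size depends on inputs nobody has.** Visit 4 is the fitting visit and is aided only, so its correlation with the Month 3 difference is unknown. A strong baseline predictor would help the SAP model. If baseline correlates 0.7 with benefit and 0.5 to 0.6 with Visit 4, then with 4 missing the bias falls to about +1.7 and error to about 7–9% (ρ = 0.7), or about +0.8 and 3–5% (ρ = 0.5). This stands, and the figures are an illustration rather than a forecast.

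**Conclusion.** The point holds as a risk the plan leaves open. Withdrawal of implanted subjects after Visit 4 is permitted, no later performance testing is provided for, and the imputation model omits the one on-device score available. Any loss related to early performance, whether by dropout or by decision, would go uncorrected.

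Under poorest-first loss, ρ of 0.3 to 0.7, SD 15 and a weak baseline predictor, complete-case bias is about +0.5 to +1.0 with 1 of 20 missing and +1.5 to +3.5 with 4 missing. Type I error is about 3–5% and 6–17%. Imputation on the SAP predictors leaves most of the bias; a strong baseline predictor reduces it considerably. Random withdrawal gives none. At the planned mean of 12 the test usually succeeds anyway, so the main harm is an inflated estimate.

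The documents do not support saying that the primary result is biased, because that requires losses that are in fact related to Visit 4 performance. Adding Visit 4 corrects the bias only if loss depends on data in the model. The change is worth making because the score is already collected.

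**What to change.** 1. **SAP 6.6.1.2.** Add the Visit 4 aided adaptive speech-in-noise score to the PROC MI predictors, and say how a missing Visit 4 score is handled (for example, imputed jointly). Cost: one more predictor with about 16 to 20 observed subjects. With 16 observed, residual degrees of freedom go from 16 − 4 = 12 to 16 − 5 = 11. State which degrees of freedom the pooled test uses.
2. **Protocol 7.2.6.** Ask every withdrawn implanted subject who consents to further contact to complete the existing Visit 5 aided and unaided QuickSin, whatever the reason for withdrawal. State that a protocol deviation alone does not end outcome collection. The listed reasons can stay as recording categories. Cost: a short amendment, matching consent wording, and a few deviating subjects kept in the data. No new visit or test is needed.
3. **SAP 6.6.1.1.** Reconcile the complete-data wording with SAP 6.2 and 6.6.1.2 and Protocol 9.5, so that the imputed analysis applies to the primary endpoint. If the complete-data wording governs, the first change does nothing for the primary test.

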7.2.7 Randomization Procedures

Subjects who meet eligibility criteria for enrolment will be randomized to a test order for the 3-month interval prepared by the Sponsor. Subjects will be randomly assigned to one of two test order configurations using a ratio of 1:1.

7.2.8 Blinding Procedures

Not applicable for the current clinical investigation.

7.2.9 Post-investigation Medical Care

Not applicable for the current clinical investigation.

7.3 Performance Evaluations and Procedures

7.3.1 Metrics

7.3.1.1 Audiometric Thresholds

7.3.1.1.1 Unaided audiometric thresholds

Unaided audiometric thresholds will be obtained for each ear, with insert earphones or headphones, using the standard audiometric technique for pure-tone air-conduction testing. All preimplantation testing will be completed using an audiometer calibrated to American National Standards Institute (ANSI) standards with maximum output for frequencies of 0.5 to 4 kHz. Pure tone threshold exploration will be completed using the adaptive Hughson &

Westlake procedure¹.

Testing in each ear will include the following:

Air conduction thresholds: 250, 500, 1000, 2000, 3000, 4000, 6000, 8000 Hz with appropriate masking as required;

Bone conduction thresholds: 250, 500, 1000, 2000, 3000 & 4000 Hz with appropriate masking as required.

NOTE: An audiogram completed up to 90 days prior to Screening will be considered valid for determination of eligibility and data collection as part of Screening if all required frequencies detailed above were assessed.

7.3.1.1.2 Aided audiometric thresholds

Aided audiometric thresholds will be obtained in a calibrated sound field, using the standard audiometric technique for sound field testing. The purpose of this assessment is to establish hearing thresholds in the free-field through a speaker in the front position (0° azimuth). All testing will be completed using narrow band noise in a sound field calibrated to American National Standards Institute (ANSI) standards with maximum output for frequencies of 0.5 to 4 kHz. The test shall be performed with the non-test ear blocked. Testing will include the following:

Aided sound field thresholds: 500, 1000, 2000, 4000, 6000Hz.

7.3.1.2 Speech perception in quiet

7.3.1.2.1 CNC Monosyllabic Words

The CNC Word Test² is a validated test used clinically and in research to assess the performance of adults with hearing loss on open-set word recognition. The test consists of 10 recorded lists of 50 monosyllabic words in CD format. Two lists will be administered in quiet at a level equal to 60 dBA in the sound field and scored as total number of words and phonemes correct, which will be expressed as a percentage correct for this study. Subjects will be tested using a configuration of speech at 0° azimuth in quiet (S0). The test shall be performed with the non-test ear blocked. Visit 1 will be performed in the unaided and aided condition using the Baha 5 Power on a Sound Arc. Visits 4, 5, and 6 will be performed using the Osia 2 Sound Processor.

7.3.1.3 Speech perception in noise

7.3.1.3.1 AzBio Sentences in Noise

The AzBio Sentence Test³ is a validated test used clinically and in research to assess the open-set sentence recognition in speech-weighted noise of adults with hearing loss. It consists of 15 lists of 20 sentences each. AzBio sentences are spoken by different talkers in a conversational style with limited contextual cues that the listener can use to predict or 'fill in' unintelligible words. The sentences will be presented at a fixed level of 65 dBA at a fixed +5 dB signal-to-noise ratio (SNR) using the accompanying noise stimulus. Each list includes

5 sentences from 4 different male and female speakers. The average level of intelligibility of each list is 85% +/- 1%. Each word in the sentence counts towards the overall score (percent correct). Subjects will be tested using a configuration of speech and noise at 0° azimuth (S0N0). The test shall be performed with the non-test ear blocked. Visit 1 will be performed in the unaided and aided condition using the Baha 5 Power on a Sound Arc and Visit 5 will be performed using the Osia 2 Sound Processor.

7.3.1.3.2 QuickSin

The QuickSin⁴ was developed to provide a quick way for clinicians to quantify a patient's ability to hear in noise, determine if extended high frequency emphasis improves or degrades understanding of speech in noise and provide a large number of equivalent test lists for use in clinical and research work. Each track consists of six sentences with five key words per sentence presented in four-talker babble noise. The sentences are presented at signal-to- noise ratios which will be decreased manually in 5-dB steps from 25 (very easy) to 0 (extremely difficult). The SNRs used are: 25, 20, 15, 10, 5 and 0, encompassing normal to severely impaired performance in noise. Subjects will be tested on 4 individual tracks (24 sentences) at 65dB(A) using a configuration of speech at 0° and noise at 180° azimuth (S0N180) for each condition. The split noise tracks are numbered 24 – 35. The test shall be performed with the non-test ear blocked. Visit 1 will be performed in the unaided and aided condition using the Baha 5 Power on a Sound Arc. Visits 4, 5, 6 will be performed using the Osia 2 Sound Processor.

